The principal investigator will be responsible for the overall monitoring of the data and safety of study participants. The principal investigator will be assisted by other members of the study staff. Complications related to placement of an arteriovenous graft for hemodialysis, such as graft thrombosis and graft infection with/without systemic infection, will be closely tracked. All vascular access-related clinical events will be adjudicated (based on standards of care) by the patient's nephrologist and treating physicians. Events will be recorded electronically and reported to the principal investigator monthly. An independent Safety Officer, unblinded to treatment assignments, will review the following vascular access-related events on a quarterly basis: primary access failure, access infection (local and systemic), access thrombosis, and arterial steal syndrome. All concerns regarding the frequency of arteriovenous graft-related complications will be reported to the Wake Forest IRB. In addition, the principal investigator, Safety Officer, and members of the research group will carefully consider amendments (including halting the trial if necessary).

Reporting of Unanticipated Problems, Adverse Events or Deviations (Appendix E)

The principal investigator along with the research staff will be responsible for periodic evaluation of clinical trial data to ensure continued participant safety, protocol compliance, data collection as well as scientific validity. Adverse events are not anticipated, but any occurring will be documented and reported according to WFSM IRB policies and procedures. Cumulative adverse events and study progress summary will be communicated to the IRB at the time of continuing review. Protocol violations and expected procedure-related events (i.e., having a potentially causal relationship to the strategy) occurring within 7 days of an access intervention will be collected.

All deaths occurring during the trial period will be collected. The cause of death will be determined by the patient's nephrologist and/or primary team according to standard practice. Deaths will be classified into one of six categories: cardiovascular, infectious, malignancy-related, elective withdrawal from dialysis, sudden death at home, or other). After deaths are classified into these categories, they will be further classified as to whether the death was access-

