related. Deaths will be considered access-related if resulted from a direct complication of the access or an access-related procedure (e.g. complications of catheter-related bacteremia leading to death). Access-related deaths will be further sub-classified as index fistula-related, index graft-related or catheter-related deaths. All vascular access-related clinical events will be adjudicated (based on standards of care) by the patient's nephrologist and treating physicians. Events will be recorded electronically and reported to the PI monthly. An independent Medical Safety Officer ([name]), unblinded to treatment assignments, will review the following vascular access-related events on a quarterly basis: primary access failure (i.e., permanent access failure before hemodialysis suitability), access infection (local and systemic), secondary access failure (i.e., permanent access failure after was used for hemodialysis), and arterial steal syndrome. Any unanticipated problems, serious and unexpected adverse events, deviations or protocol changes will be promptly reported by the PI or designated member of the research team to the IRB and the NIA government agency as appropriate.

Appendices

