Appendix E. Protocol Violation, Expected Events, Cause of Death

A. Protocol violations	
Dropouts and their causes (e.g., withdrawal of consent, transfer to another center, refusal to undergo study-specific assessments)	
B. Expected procedure-related events	
Local events	Systemic events
Bleeding from access site requiring intervention	Allergic reaction to local anesthetic
Nerve injury	Allergic reaction to generalized anesthetic
Ischemia (to nerves or distal extremity)	Heart failure (high output congestive heart failure)
Arterial steal syndrome requiring intervention	Myocardial infarct
Seroma	Pulmonary embolism
	Aspiration pneumonia
	Nosocomial infection
	Sudden death
C. Classification of causes of death	
1. Cardiovascular	
Acute coronary syndromes and related complications	
Heart failure	
Cardiac dysrhythmias	
Valvular disorders	
Myocardial disorders	
Pericardial disorders	
Complications of cardiac or vascular surgery	
Complications of cardiac or vascular procedures	
Cardiac perforation following hemodialysis catheter insertion	
Cardiac arrest during placement of a dialysis catheter in radiology suite	
Acute stroke syndromes and complications (ischemic and hemorrhagic)	
Complications of peripheral vascular disease (examples: ischemic gut, ischemia of the extremities)	
Complications of aortic dissection and aortic aneurysm	
Complications of congenital heart disease	
2. Sudden death at home	
without antecedent illness or procedure that could have contributed to the death.	
3. Infectious	
Bacteremia/sepsis from any source, including complications of vascular access.	
Examples of sources of sepsis: pneumonia, urinary tract, infective endocarditis, intra-abdominal abscess, colitis, septic joint, soft tissue ulcer, dialysis vascular access related bacteremia, dialysis vascular access related sepsis and infective endocarditis, dialysis vascular access related sepsis and osteomyelitis, dialysis vascular access related sepsis and ectopic abscess, infective endocarditis of mechanical valve from infectious complication of dialysis vascular access, etc.	
4. Malignancy-related	
Complications of any malignancy leading to death. This includes metastatic disease leading to withdrawal of care or palliation.	
5. Elective withdrawal from dialysis	
Elective discontinuation of dialysis therapy, in the absence of an acute, antecedent precipitant such as	

an acute medical illness.

6. Other:

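### Deaths and serious expected peri-operative events are not on the Safety Officer's quarterly list, and pre-listing them as expected leaves their reporting time unstated

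*Combined protocol and SAP*

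**What the plan says.** **Prompt reporting.** The section on reporting of unanticipated problems, adverse events or deviations states: "Any unanticipated problems, serious and unexpected adverse events, deviations or protocol changes will be promptly reported by the PI" or a designated team member, to the IRB and the NIA as appropriate.

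**Other reporting.** The same section says "Adverse events are not anticipated, but any occurring will be documented and reported" under the institution's IRB policies, and "Cumulative adverse events and study progress summary will be communicated to the IRB at the time of continuing review". Expected procedure-related events "occurring within 7 days of an access intervention will be collected"; that sentence sets no reporting time.

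**Expected events.** Appendix E has a part headed "B. Expected procedure-related events". Its systemic column includes "Myocardial infarct", "Pulmonary embolism" and sudden death. This last entry is separate from the cause-of-death category for sudden death at home.

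**Independent review.** Under Data and Safety Monitoring, an independent, unblinded Safety Officer reviews these events quarterly: "primary access failure, access infection (local and systemic), access thrombosis, and arterial steal syndrome". The reporting section repeats the arrangement but has secondary access failure where the first list has access thrombosis.

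**Deaths.** All deaths are collected, with the cause assigned by treating clinicians. They are classed as access-related or not, and access-related deaths are attributed to the index fistula, the index graft or a catheter. No sentence sends deaths or this classification to the Safety Officer.

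**The concern.** The trial randomises an operation in people aged 65 or over with end-stage or advanced kidney disease, some of whom take part through a legal representative. Death and major cardiovascular events soon after surgery are the gravest harms that could differ between arms.

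Two features of the plan work against seeing them. Labelling an event as expected takes it out of the explicit prompt-reporting wording, however serious it is. And the one person the plan calls independent is scheduled to see access failure, infection, steal and (in one list) thrombosis, but not deaths. That person also shares in considering amendments to the trial, including halting it. A difference in mortality between arms would reach that person only if someone chose to send it.

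**Working it through.** No figure in the plan bears on this point, so the check is a comparison of texts. Each type of event is followed through the stated routes.

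| Event after study surgery | Explicit prompt-reporting sentence | Quarterly Safety Officer list | Other stated routes |
|---|---|---|---|
| Myocardial infarction, pulmonary embolism or sudden death within 7 days | Serious but pre-listed as expected; caught only if judged an unanticipated problem | Named on neither list | Collected; IRB policies (content not given); cumulative summary at continuing review |
| Death from a cause not in part B, for example stroke | Caught as serious and unexpected | Death named on neither list | As above for IRB policies and summary; all deaths collected |
| Fatal access infection | Depends on how it is classed (part B lists nosocomial infection) | The infection is on both lists; the death is not | As above; all deaths collected |
| Arterial steal needing intervention | Pre-listed as expected | Steal is on both lists | As above |

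Four results follow.

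1. **Reporting time.** For the first row, the sentence that requires prompt reporting does not apply through its serious-and-unexpected limb. The remaining routes either state no time, refer to policies outside the documents, or wait for continuing review.
2. **Independent review.** In the first three rows, the death or major event is not itself a scheduled item. The fatal infection reaches the Safety Officer as an infection, not as a death.
3. **Expectedness.** Saying that adverse events are not anticipated conflicts with an appendix of expected events, and sits badly with the moderate-risk rating under Human Subjects Protection. If the phrase governed, every serious event would count as unexpected and be promptly reportable. If Appendix E governs, the part B events would not. The protocol does not say which applies.
4. **The two lists.** Three items are common to both (primary access failure, access infection, steal). The fourth is access thrombosis in one and secondary access failure in the other.

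**Illustration only.** The documents give no peri-operative risk. Assume a risk p per participant of death soon after surgery from a pre-listed cause, with all 50 planned participants operated on and outcomes independent. The chance of at least one such death is 1 − (1 − p)^50:

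- p = 0.5%: 1 − 0.995^50 = 22%
- p = 1%: 1 − 0.99^50 = 39%
- p = 2%: 1 − 0.98^50 = 64%
- p = 5%: 1 − 0.95^50 = 92%

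Over this assumed range, the unclear reporting rule could come into use even in a pilot of this size. The textual finding does not depend on it.

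**The case against.** The strongest reply is that the protocol has more routes than the one sentence. Any adverse event is reported under the institution's IRB policies, which may set a short deadline for deaths. Unanticipated problems form a separate limb of the prompt-reporting sentence. A death from an unlisted cause remains serious and unexpected. All of this stands. A reader might infer that a peri-operative death triggers no prompt reporting at all; the documents do not support that. They show only that the timing for a pre-listed event is not stated in the protocol.

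A reader might also infer that any decision to halt would be taken without knowledge of deaths. That is not supported either. Those who would consider halting are the principal investigator, the Safety Officer and the research group together. The principal investigator carries overall safety responsibility, and the study collects and classifies all deaths. Nor does anything bar the Safety Officer from seeing further material.

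Finally, this is a 50-participant pilot in people already judged to need an access, and extra prompt reports may duplicate IRB rules. That argues for aligning the wording with those rules. It does not answer the review gap: the cited policies are invoked for adverse event reporting, and nothing in the documents indicates that they place deaths before this trial's Safety Officer.

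**Conclusion.** The point holds in two parts. The firmer part is that neither statement of the quarterly list schedules deaths, myocardial infarction or pulmonary embolism for review by the only independent, unblinded monitor, although the data are already collected. The second is that a pre-listed event, including sudden death, lies outside the explicit serious-and-unexpected wording. Unless it is judged an unanticipated problem, its reporting time rests on policies not in the documents. The statement that adverse events are not anticipated, and the mismatch between the two lists, are contradictions to be reconciled.

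The size is a missing scheduled route and an ambiguous rule, not a number of events. Confidence is medium, because the unseen IRB policies could close the reporting part. The change is worth making because it is cheap and concerns the most serious outcomes.

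**What to change.** - Use one Safety Officer list in both sections, containing both access thrombosis and secondary access failure. Add all deaths, with their access-related classification, and serious Appendix E part B events, tabulated by arm.
- State that part B defines what is collected and does not exempt a death or serious event from prompt reporting. Give the timing, aligned with the IRB policy.
- Delete the phrase saying that adverse events are not anticipated, and keep the commitment to document and report them.

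The cost is protocol wording, a few more lines in a quarterly listing and a small number of additional prompt reports. No new data collection is needed, and the change introduces no stopping rule.

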Appendix A: Study Flow Diagram

[figure not shown]
Appendix B : Assessment Instruments

Appendix C : Schedule of Assessments

Appendix D: Vascular access outcomes

Appendix E: Protocol Violation, Expected Events, Cause of Death

Appendix A: Study Flow Diagram

Appendix B: Assessment Instruments

- 1) **Grip Strength Test:** a muscle strength test that uses a hand-held dynamometer to assess the upper arm grip-strength in each arm. Study participant will squeeze the dynameter as hard as possible two separate times for each arm.
- 2) The four meter gait speed (4MGS) will be assessed on a flat, unobstructed four meter delineated course by trained research staff following a standard operating procedure. Participants will be asked to walk at their usual pace from a standing start. Two trials will be completed. The arithmetic mean of the two trials will be used for analysis. Participants will be allowed to use their usual walking aids and ambulatory oxygen, with the cylinder carried by an assistant and these factors will be kept constant within person measurements on repeated walk tests. To express gait speed in ms-1, distance walked (i.e. 4 meters) will be divided by time expressed in seconds.
- 3) **Short Form Vascular Access Questionnaire (SF-VAQ):** a questionnaire that the study participant will complete that measures the participant's satisfaction with their vascular access. Participant will circle a number on the scale that indicates their level of agreement with each statement regarding physical symptoms, social functioning, complications and overall satisfaction.
- 4) **Verbal Descriptor Scale (VDS):** a scale the study participant will complete that measures their pain at the AV access site. The participant will rate their pain as either absent/no pain, mild pain, moderate pain, or severe pain/pain as bad as could be/extreme pain.
- 5) **modified Abbey Pain Scale (mAPS) :** a scale used for people who cannot verbalize that measures their pain at the AV access site. The study staff will score the scale by observing the participant's vocalization, facial expression, and body language.
- 6) **Activities of Daily Living (ADL) and Instrumental Activities of Daily Living (IADL):** these two scales measure the level of independence of the study participant. For the ADL scale, study staff will ask participants how well they can perform various daily activities such as bathing, grooming, dressing, eating, etc.

For the IADL scale, study staff will ask participants how well they can perform various daily activities such as housekeeping, food preparation, shopping, etc.

- 7) **Kidney Disease Quality of Life instrument short form (KDQOL-SF) version 1.3:** this survey consists of a generic core (Short Form-36 [SF-36]) and an 11-item kidney disease-specific scale. This survey will be completed by the study participant and asks a wide variety of questions about their health and quality of life.
- 8) **Qualitative Study Interview:** this interview will consist of questions regarding the participant's study experience (study conduct, intervention outcomes, and intervention decisions).

Appendix C: Schedule of Assessments

Schedule of assessments						
Assessment	Enrollment	Week 1 or 2 after AV access placement	Week 3 after AVG placed or Week 4 after AVF placed	Week 5 or 6 after first AV access cannulation	Week 24 or 25 of AV access use	Week 24 or 25 after AV access placement if primary AV access failure
Grip strength	√	√	Evaluation at DAG to assess AV access development and suitability for cannulation	√	√	√
4MGS	√			√	√	√
VDS or mAPS		√		√	√	√
SF-VAQ		√		√	√	√
ADLs and IADLs	√				√	√
KDQOL-SF 1.3.	√				√	√
Qualitative Study Interview						
AV, arteriovenous; 4MGS, four meter gait speed; VDS, Verbal Descriptor Scale; mAPS, Modified Abbey Pain Scale; SF-VAQ, Short-form vascular access questionnaire; ADLs, Activities of daily living; IADLs, Instrumental ADLs; KDQOL-SF, Kidney Disease Quality of Life Short-form. The Qualitative Study Interview will be performed on a maximum number of 10 subjects who have been enrolled in study >6 months and have had AV access surgery and are still currently enrolled in study either during a study visit or before the subject's dialysis treatment at their respective dialysis center.						

Appendix D. Vascular access outcomes

Vascular access outcomes (according to the recommendations of the Committee on Reporting Standards for Arteriovenous Accesses, Society for Vascular Surgery and American Association for Vascular Surgery)	
AV access outcome	Definition
Primary access failure	Permanent failure of the fistula or graft before hemodialysis suitability. This includes inadequate maturation, thrombosis, failure of first and subsequent cannulations, and other complications leading to nonfunctional fistula or graft.
Successful cannulation	The arteriovenous access became the primary vascular access for hemodialysis (the fistula or graft access has been cannulated with two 16- or 15-gauge needles for ≥ 3 consecutive dialysis sessions and the TCVC was removed).
Suitability for hemodialysis	Fistula or graft use with two needles and maintenance of blood flow $\geq 300\text{ml}/\text{min}$ for $\geq 75\%$ of dialysis sessions over a continuous 4-week. The maturation criteria can be satisfied at any time within 6 months of fistula or graft creation surgery.
Unassisted access maturation	Criteria for fistula or graft suitable for hemodialysis (based on the above criteria) are met before any endovascular or secondary surgical procedure to facilitate maturation.
Assisted access maturation	Satisfaction of the criteria for fistula or graft suitability for hemodialysis after a procedure to facilitate maturation (e.g., angioplasty, stent placement, surgical revision, ligation of accessory veins).
Primary access patency	Intervention-free access survival defined as the time from fistula or graft creation to any intervention to maintain patency.
Secondary access failure	Permanent failure after the fistula or graft met dialysis suitability criteria with subsequent abandonment.
Noninfectious complications	Stenosis, thrombosis, hand ischemia, aneurysm, pseudoaneurysm, infiltration.
Infectious complications	Fistula or graft cellulitis, abscess, bacteremia.
Access procedures	Angioplasty, stent placement, surgical revision, ligation of accessory veins, superficialization of vein.
Other clinical outcomes	TCVC placement, new AV access surgical creation, AV access-related hospitalization or death.
Limb ischemia following AV access placement	
Symptoms	Paresthesia, pain, hand stiffness, ulceration and tissue loss in the limb with arteriovenous access.
Physical examination	Diminished or absent radial pulse, pallor, diminished sensation, and, in advanced stages or severe cases, ulceration and gangrene.
Grade 1, mild	Cool extremity with few symptoms but steal demonstrable by flow augmentation with access occlusion.
Grade 2, moderate	Intermittent ischemia only during dialysis/claudication.
Grade 3, severe	Ischemic pain at rest/tissue loss.
TCVC access outcome	Examples

Infectious complications	Catheter exit site infection, tunnel infection, bacteremia.
Non-infectious complications	Catheter malposition, mechanical dysfunction, catheter migration, venous thrombosis, pneumothorax, hemothorax, arterial puncture.

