The benefits of AVF over AVG are least certain in older adults, as age-related biological changes independently modulate patient outcomes.¹⁰ Nationally representative cohort studies of older adults with incident ESKD have shown similar patient survival between those whose first AV access placed or used was a fistula or a graft.^{11,12} Compared with grafts, fistulas fail more often and necessitate longer times and more subsequent procedures to aid development, exposing older patients to time-consuming procedures that may negatively affect upper extremity strength and erode their quality of life.¹³⁻¹⁶ Hitherto, the contribution of pre-operative muscle strength to AV access outcomes and the impact of AV access placement on upper extremity strength and self-sufficiency have not been evaluated. We propose a randomized pilot trial in older adults with pre-dialysis advanced chronic kidney disease (CKD) or incident ESKD using a TCVC for HD who had no prior AV access surgery and have upper extremity vasculature suitable for either fistula or graft placement. Participants will be randomized to receive an upper extremity AVF-first or AVG-first access for HD.

Objectives

The primary objective of this study is to prospectively evaluate patient and vascular access outcomes in a randomized intervention and in a patient population in whom fistula-first guidelines have been applied despite the lack of proven benefit and at the detriment of more access failures and procedures. Our hypothesis is that there is a bidirectional relationship between the type of first AV access and patient outcomes as follows: a) the graft-first strategy will confer a more effective transition from TCVC-based to AV access-based HD and will limit upper extremity functional impairment from protracted access development and subsequent access procedures, and b) preoperative muscle strength will impact AVF development.

Methods and Measures

Design

This randomized pilot trial will be parallel-arm in design (Appendix A). We plan to enroll 50 patients of age ≥ 65 years, with incident ESKD or advanced CKD expected to require HD initiation within 90 days of screening. Screening for potential participants will be performed

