in two stages. In the first stage, all patients ≥ 65 years old receiving chronic HD and use a TCVC will be screened for eligibility. Of these patients, only those who did not have a previous AV access surgery and are considered for AV placement (according to goals of care established by the patient's nephrologist) will be maintained as potential participants and advanced to the second phase of screening pending determination of surgical eligibility for placement of upper extremity AVF and AVG. Ultrasound vascular mapping of both upper extremities to assess vascular anatomy is routinely performed pre-operatively at our institution. Arterial diameter of ≥ 2 mm and vein diameter of ≥ 2.5 mm at the site of AV anastomosis indicate suitability for AVF surgical creation.⁷ To complete the eligibility criteria, patients must have proper anatomy (in either upper extremity) for placement of AVF (forearm or arm) and AVG (forearm or arm).

Setting

Participant recruitment will occur at Wake Forest Baptist Medical Center (WFBMC) Outpatient Nephrology Clinics, WFBMC Inpatient Nephrology Service, Wake Forest Outpatient Dialysis (WFOPD) units or any other Wake Forest affiliated institution (i.e., High Point Regional Medical Center).. After the screening process identifies a potential study candidate, the patient will be approached for study participation. The study coordinator and/or the PI and/or other study member will contact the patient and present an overview of the study. This will be done either in person, by phone, or electronically (e.g., Skype or Facetime). When the patient presents interest in the study after the initial overview, the study coordinator and/or the PI or other study team member will meet in person with the potential study participant to further review the study and the informed consent to patient's and/or patient's family member/representative full understanding, and finalize the enrollment.

Subjects selection criteria

The overall eligibility will be reached as a consensus between the PI and the vascular surgeon.

Inclusion Criteria

1. Age ≥ 65 years

2. Incident ESKD on chronic HD and recovery of kidney function is unlikely or advanced CKD expected to require HD initiation within 90 days of screening and deemed medically necessary by the treating nephrologist to proceed with AV access placement (either AVF or AVG) in preparation for HD initiation
3. TCVC is the sole vascular access used for HD

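### Appendix D counts the six-month suitability window from surgery, so a pre-dialysis participant who starts HD after about day 154 cannot be classed as suitable or matured, however good the access

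*Combined protocol and SAP*

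**What the plan says.** **Outcome definition.** Appendix D makes suitability depend on actual use: "Fistula or graft use with two needles and maintenance of blood flow" of at least 300 ml/min, in at least 75% "of dialysis sessions over a continuous 4-week" period. The time limit follows: "The maturation criteria can be satisfied at any time within 6 months of fistula or graft creation surgery". No other starting point is given.

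**Outcomes built on it.** Unassisted and assisted maturation apply the same criteria before or after a facilitating procedure. Primary failure is permanent failure before suitability; secondary failure is permanent failure after suitability was met.

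**Who is enrolled.** The Background section describes "older adults with pre-dialysis advanced chronic kidney disease (CKD) or incident ESKD using a TCVC for HD". Inclusion criterion 2 admits "advanced CKD expected to require HD initiation within 90 days of screening". The Design, Interventions and Subject Recruitment sections also name pre-dialysis or advanced CKD patients. Inclusion criterion 3, however, reads "TCVC is the sole vascular access used for HD", and Subject Recruitment lists catheter use for HD as a further requirement.

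**Follow-up and data.** The Analytical Plan follows participants for at least 12 months from index placement. The date of HD commencement is listed among the enrollment data. After the week 3 or 4 access evaluation, the Appendix C visits depend on cannulation, on access use, or on primary failure. No visit is defined for a patent access not yet in use.

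**The concern.** For a participant already on HD, six months from surgery is a workable limit on access development. For a participant not yet on HD, the same limit also measures how soon the kidney disease progressed to dialysis. The 90 days in inclusion criterion 2 is a forecast at screening, and no rule removes, censors or re-times someone whose HD starts later. A well-developed access in such a participant cannot supply four weeks of sessions inside the window.

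Two things are at stake. The suitability and maturation proportions passed to the larger trial would be somewhat too low, for a reason unrelated to the access. And the failure categories become inconsistent for an access first used after month 6 and then lost: the Safety Officer's quarterly review counts primary and secondary failure, and the two parts of the document would place that event in different categories.

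**Working it through.** **The plan's own figure.** The only statistical design figure is the 0.138 error margin for the consent and surgery rates. 1.96 × √(0.25/50) = 0.1386, so it reproduces (truncated). It does not bear on this point, and the plan states no suitability rate.

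**Cut-off.** Window: 6 months ≈ 182 days from surgery (Appendix D). Required run: 4 weeks = 28 days (Appendix D). Latest first HD session that still allows suitability: 182 − 28 = day 154 after surgery. This is the most favourable case, because it assumes qualifying use from the first session. If the run needed only to begin inside the window, the cut-off would move to day 182 and the gap would remain.

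**If the forecast is met.** Let surgery fall s days after screening and HD start on day 90 after screening. With qualifying use from the first session, the run ends max(90 − s, 0) + 28 days after surgery. The slip past day 90 needed to make suitability impossible is s + 154 − 90 days.

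| s (days) | Run ends, days after surgery | Slip needed (days) |
|---|---|---|
| 0 | 118 | 64 |
| 30 | 88 | 94 |
| 60 | 58 | 124 |
| 90 | 28 | 154 |

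Every on-forecast start fits the window.

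**How many slip that far.** The documents give no distribution of HD start, so this part is assumption. With exponential time from screening to HD and median m, the probability of missing the cut-off is 0.5^((s + 154)/m), and the share starting after day 90 is 0.5^(90/m).

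| m (days) | s = 30 | s = 60 | s = 90 | Share starting after day 90 |
|---|---|---|---|---|
| 60 | 0.119 | 0.084 | 0.060 | 0.35 |
| 90 | 0.242 | 0.192 | 0.153 | 0.50 |
| 180 | 0.492 | 0.439 | 0.391 | 0.71 |

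The last two rows suppose that half or more of the 90-day forecasts fail, which fits poorly with inclusion criterion 2. The 60-day row is the more plausible guide: 6–12% of pre-dialysis participants. If 15 of the 50 were pre-dialysis (also assumed), that is 15 × 0.06 to 15 × 0.12, or 0.9 to 1.8 people.

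**Effect on the reported proportion.** Let f be the pre-dialysis share, g the share of those who start too late, and p the true suitability proportion, all assumed. The number affected is 50·f·g, and the understatement is p·f·g.
- f = 0.2, g = 0.05, p = 0.6: 0.5 people, 0.6 points.
- f = 0.5, g = 0.10, p = 0.6 to 0.8: 2.5 people, 3 to 4 points.
- f = 0.8, g = 0.30, p = 0.8: 12 people, 19 points.

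**Failure split.** Take an access first used in month 7 and then permanently lost. Under Appendix D suitability was never met, so secondary failure is excluded and the loss counts as permanent failure before suitability, that is, primary failure. The section on reporting unanticipated problems defines secondary failure as permanent failure after the access was used for HD, with no six-month limit, so there it is secondary. That section's primary-failure wording still refers to suitability, so its two categories also overlap for this access.

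**The case against.** The case for leaving the text alone has real strength.

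- **Rarity.** HD must slip roughly 64 to 154 days past the forecast before anyone is affected. This stands, and it limits the size of the problem.
- **Eligibility.** Read literally, inclusion criterion 3 would leave no pre-dialysis participants and the point would be empty. The explicit pre-dialysis wording elsewhere supports the premise, but the point is conditional on how that contradiction is reconciled.
- **Other records.** Development is examined at week 3 or 4, cannulation dates and patency are monitored throughout, and primary patency does not require HD. Late use of a good access would therefore be recorded. It would still not count towards suitability or maturation.
- **The remedy has side effects.** Running the clock from first HD gives some accesses longer to develop, which could favour fistulas, since the Background says they take longer. Starts beyond about six months after surgery also outrun the minimum follow-up. Both stand, and the fix has to deal with them.

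A reader might infer that every late starter becomes a primary failure, because Appendix D adds: "This includes inadequate maturation, thrombosis, failure of first and subsequent cannulations, and other complications leading to nonfunctional fistula or graft". The text does not support that. Primary failure needs permanent failure and a nonfunctional access, and a patent unused access is neither.

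A reader might also infer that the trial's main outcome and the muscle-strength regression are contaminated. No section ranks suitability as the main outcome, and the access outcome in the regression is not defined, so that effect is only conditional.

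**Conclusion.** The gap is real and narrow. It follows from stated rules: the window starts at surgery, the criterion needs four weeks of dialysis sessions, pre-dialysis patients are admitted, and no exception is written. Suitability and both maturation outcomes are out of reach for a participant whose HD starts after about day 154. The failure labels conflict only when an access is first used after month 6 and then lost.

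The number affected cannot be derived from the documents. The 6–12% rests on an assumed exponential time to HD with a 60-day median and surgery 30 to 90 days after screening; it rises if forecasts slip more often. A reader might take the 39–49% of the 180-day scenario as the expected loss. The documents give no support for a median twice the eligibility forecast.

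Nor do they support a claim that the arm comparison is biased. Randomization balances late starters on average, and equal late shares would shrink a difference by the factor 1 − f·g (0.95 in the middle case). No stratification by dialysis status is stated, so with 25 per arm a chance imbalance is possible. The consent and 90-day surgery endpoints are unaffected.

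**What to change.** In Appendix D and the Analytical Plan:

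1. For participants not on HD at index surgery, count the six-month suitability window from the later of access creation and first HD session, censored at end of follow-up. Keep the current window for participants already on HD.
2. Report a patent access with no or insufficient HD exposure during follow-up as not assessable, not as non-matured, with counts by randomised arm. Define insufficient in advance, for example fewer than four weeks of sessions. At the 12-month minimum, a full six-month window is observed for HD starts up to about day 183 after surgery (365 − 182), and a four-week run for starts up to day 337 (365 − 28).
3. Report suitability and maturation by HD status at randomisation. Also show the result under the surgery-anchored window with all participants as randomised, so that any gain from longer development time is visible.
4. Use one primary/secondary failure split throughout, aligned with the use-based wording in the section on reporting unanticipated problems. State what counts as used, since Appendix D treats failed first and subsequent cannulations as primary failure.
5. Record the date of first HD during follow-up, not only at enrollment.
6. Reconcile inclusion criterion 3 and the catheter requirement in Subject Recruitment with the pre-dialysis wording.

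The cost is a wording change, one added follow-up date and a second tabulation. Some pre-dialysis accesses get longer to develop, which item 3 makes visible, and some participants will be reported as not assessable.
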